8. DATA SOURCES

will develop a custom, curated dataset for this study based on longitudinal electronic medical records (EMR) data from the NATDSS, the largest cancer registry database in China. This database, established in 2018 by China National Cancer Center (NCC), covers over 1400 hospitals across 31 provinces and over 10 million cancer patients in

Statistical and Epidemiological Analysis Plan (SEAP) for Observational and Non-Interventional Studies (ONIS)

Page 15 of 36

China. This multicenter hospital-based database consists of data of 1509 variables from 7 aspects including drug, patient basic information, inpatient, outpatient, tests and examinations, treatment and follow up. NATDSS is linked with National Mortality Database from Chinese Center for Disease Control and Prevention Center (China CDC) to obtain patients' death information [R23-1183].

9. DATA MANAGEMENT AND SOFTWARE/TOOLS

9.1 SOURCE DATA

Source data from the NATDSS are collected via an automatic web-based system, coded, deidentified and transmitted in a secure manner to maintain patient confidentiality compliant with national privacy standards. Source data will be desensitized by hiding the personal identifiable information or other sensitive information to create an Enterprise Master Patient Index (EMPI), which will allow individual level data to be linked when multiple sources are involved in the data integration process.

Authorization from NCC and Independent Ethics Committee (IEC) approval of leading site will be applied to ensure that the data are accessible and continuously active during study period.

9.2 DATA CURATION

The data curation processes for this ONIS will be divided into the following parts.

- CRF generation: will design the first draft of variable list (CRF) and ensure that CRF is adequate for the collection of all relevant clinical data specified in the study protocol. CRF will be finalized after BI study team's review and confirmation.
- Data extraction: Scope of source data will be identified and extracted based on CRF and extraction plan. Data engineer from will verify critical parameters, including whether the data modules are complete, whether information for data encoding and decoding is clear, whether the mark of the data association is correct, whether the amount and characteristics of patients meet the requirements of the protocol, etc.
- Source data quality control: The source data will be evaluated across several aspects, including whether the data extraction is complete, whether the data conforms to the basic logic of medical records, and whether the threshold conforms to the normal clinical range. Regarding the data of logical value, abnormal value, and missing value, an effective data processing scheme shall be put forward. For any modification in the input process, confirmation and signature from the data engineer, as well as the reasons for the modification are required, to ensure that a complete audit trail has remained.
- Data transformation to project dataset: After data extraction is completed, multi-source data will be further standardized based on this study's design. Rules and procedures of data transformation will be reviewed and verified by medical experts and data engineers. Clinical information related to the same variable written in different terms will be standardized, normalized, and processed with logic and reasoning in medicine. The data management team will conduct a logic check on the entire finalized dataset after the extraction, where key data errors that can potentially affect this study will be corrected

Statistical and Epidemiological Analysis Plan (SEAP) for Observational and Non-Interventional Studies (ONIS)

Page 16 of 36

through appropriate procedures. Finally, the structured and standardized data will be examined by trained reviewers, and then reviewed and signed by data manager. After the data is transformed, a sample of subjects will be selected to compare with source data for double-check.

Locking of project datasets: The dataset will be locked after all data quality control
processes are met. Any update needed for the locked dataset must be approved by the data
manager and processed appropriately in accordance with the standard dataset unlocking
process.

For this study, BI will not have access to the original data. Data will be managed by Source code of data management and data analyses will be stored for at least 15 years at .

9.3 SOFTWARE/TOOLS

All computations and generation of tables, listings and data for figures will be performed using Statistical Analysis System (SAS) version 9.4 or higher (SAS). Used language and packages will be reported in the final report.

9.4 HANDLING OF MISSING VALUES

Missing data may be encountered due to the study's retrospective nature and unavailability of data in electronic medical records. The number and percentages of patients with missing data for each variable will be summarized and reported. Only partial missing dates will be imputed, and no replacement/imputation procedures will be used for defined variables.

Missing dates will be imputed as follows: If the day is missing and the month and year is complete, the day will be imputed as the 15th of the month. If day and month or year was missing, the date will not be imputed and will be reported as missing.

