9.7. DATA ANALYSIS

The statistical analysis plan for the study is summarized below. Full details of the statistical analysis will be documented in the Statistical and Epidemiological Analysis Plan (SEAP), which will be finalized before the end of data collection.

This study will be descriptive in nature.

It is anticipated that sample sizes for variables may vary due to unknown or missing data in the database. The number of patients with missing data for each variable will be summarized and reported. With the exception of the imputation of partial missing date values, no other imputation of missing values will be undertaken; however, the impact of missing data on interpretation of findings will be acknowledged and discussed in the final study report.

For all analyses, data for patients will be censored when lost to follow-up (i.e., still alive as of their last visit prior to end of study period).

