10.1 MAIN ANALYSIS

10.1.1 Analysis of primary objective

OS will be analyzed for Cohort 1. For OS calculation, the event time is the date of death recorded by the National Mortality Database from CDC. OS is defined as the time from initiation of 1L until the date of death due to any cause. Patients without death record during the study period will be censored at the last medical record during the study period.

OS will be estimated by the KM method to obtain median estimates with 95% CIs and IQRs for Cohort 1, calculated using the log-log transformation. OS rate at 6, 12, 18, and 24 months will be described according to the survival curves if reached.

OS may be assessed by LOT and type of treatment received in each LOT, pending feasibility. OS by LOT is defined as the time from initiation of each LOT until the date of death due to any cause.

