10.1.2 Analysis of secondary objectives

Survival after initial diagnosis will be estimated by the KM method to obtain median estimates with 95% CIs and IORs for Cohort 1 and Cohort 2.

Treatment patterns for Cohort 1 and Cohort 2 will be described by the number of lines, count with percentage (%) of patients by treatment lines, type of therapy and therapy regimens in each line.

LOTs are defined by the temporal relationship and sequencing of treatment regimens by using the dates of initiation and discontinuation of chemotherapy, targeted therapy, and/or immunotherapy. For each patient, 1L treatment regimen is defined as the first systemic treatment of any chemotherapy, and/or targeted drugs given to a patient after advanced or metastatic DDLPS diagnosis. A treatment line is advanced to the next line when a patient initiates new combinations of drugs or has the evidence of progression of disease. The start date of each LOT is defined as the date of initiation of new regimen, and the end date of each LOT is defined as the date of last dose prescribed or recorded at/before discontinuation.

Statistical and Epidemiological Analysis Plan (SEAP) for Observational and Non-Interventional Studies (ONIS)

Page 18 of 36

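### SAP 9.4 sets every missing day to the 15th without bounding it by known dates in the same month, so date order can reverse and line numbering, cohort entry and durations can be wrong

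*SAP*

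**What the plan says.** SAP 9.4 gives two rules for incomplete dates. With only the day missing: "If the day is missing and the month and year is complete, the day will be imputed as the 15th of the month". With more missing: "If day and month or year was missing, the date will not be imputed and will be reported as missing". Protocol 9.7 allows no other imputation ("With the exception of the imputation of partial missing date values, no other imputation of missing values will be undertaken") and gives no algorithm of its own.

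The definitions that use these dates rely on their order:

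- **1L and cohort.** SAP 10.1.2 defines the 1L regimen as "the first systemic treatment of any chemotherapy, and/or targeted drugs given to a patient after advanced or metastatic DDLPS diagnosis". SAP 6.3 makes the 1L start the Cohort 1 index date and uses 1L initiation to separate Cohort 1 from Cohort 2.
- **Line end.** In SAP 10.1.2, "the end date of each LOT is defined as the date of last dose prescribed or recorded at/before discontinuation".
- **Primary outcome.** In SAP 10.1.1, "OS is defined as the time from initiation of 1L until the date of death due to any cause", and "the event time is the date of death recorded by the National Mortality Database from CDC".

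SAP 9.2 provides for a logic check of the finalised dataset, correction of key errors and comparison of a sample with source. SAP 11 adds checks of code validity and missing values, tabulation of all variables and review of each distribution. None of this text mentions imputed dates, a required date order, or what to do when dates conflict.

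**The concern.** A fixed mid-month day is harmless when the neighbouring dates are months away. It is not harmless when a known date lies in the same month. There are three cases:

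- **Diagnosis after first dose.** The advanced diagnosis is recorded as June with no day, and the first dose was given on 8 June. The diagnosis becomes 15 June, so the 8 June dose no longer counts as "given to a patient after advanced or metastatic DDLPS diagnosis". The index date moves to the next dose. If the patient had already switched, the second regimen is labelled 1L. If there is no later dose, the patient leaves Cohort 1.
- **Stop before start.** A line starts on 20 June and its last dose is recorded as June. The stop becomes 15 June and the duration is −5 days.
- **Death before index.** Index is on the 20th and death is in the same month with no day. OS is −5 days. The same happens if the index day is missing and death is on the 10th.

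The first case matters most because it yields a plausible but wrong record. The other two give impossible values, and an analyst would have to choose between dropping, truncating and re-dating them after seeing the data.

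**Working it through.** The plan gives no figure to reproduce here. The inputs are the 15th rule (SAP 9.4) and exponential survival with medians of 8, 10 and 12 months (Protocol 9.5). Three inputs are not in the documents and are assumed: the share of partial dates, the diagnosis-to-1L lag and the line duration.

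**Step 1. Two dates in the same month.** Take all day pairs with the first date no later than the second, each equally likely. A month of L days has L(L+1)/2 pairs.

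- Earlier date partial: the order reverses when the later day is before the 15th, which is 14 × 15/2 = 105 pairs.
- Later date partial: the order reverses when the earlier day is after the 15th, which is (L−15)(L−14)/2 pairs.

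| L | Pairs | Earlier date partial | Later date partial |
|---|---|---|---|
| 28 | 406 | 105/406 = 25.9% | 91/406 = 22.4% |
| 30 | 465 | 105/465 = 22.6% | 120/465 = 25.8% |
| 31 | 496 | 105/496 = 21.2% | 136/496 = 27.4% |

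A dose on the 15th itself is counted here as not reversed.

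**Step 2. Overall frequency.** This needs an assumed lag distribution. The figures below are by simulation with a 30-day month and a uniform day for the first date, per patient with that date partial. The exponential is gamma shape 1.

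| Interval (partial date) | Mean, days | Shape 1 | Shape 2 | Shape 3 |
|---|---|---|---|---|
| Diagnosis to 1L (diagnosis) | 30 | 10% | 5% | 3% |
| Diagnosis to 1L (diagnosis) | 45 | 7% | about 2.5% | 1% |
| Line start to stop (stop) | 60 | 6% | about 2% | 0.6% |
| Line start to stop (stop) | 90 | 4% | 0.8% | 0.2% |

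The exponential puts most weight on very short lags and so gives the highest figures. The result depends on shape as much as on the mean.

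**Step 3. Death before index.** At medians of 8, 10 and 12 months, about 4.3%, 3.5% and 2.9% of patients die in the calendar month of index. The order reverses in about 1.1%, 0.9% and 0.8% if the death day is missing, and in 1.0%, 0.8% and 0.7% if the index day is missing.

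**Step 4. Effect on median OS.** Take the extreme case: every death day is missing and every reversed case is dropped. If a fraction p of patients is removed, all of them early deaths, the new median is m × [1 − ln(1 − p)/ln 2].

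- m = 8, p = 0.0114: 8 × (1 + 0.01147/0.6931) = 8.13 months.
- m = 12, p = 0.0076: 12 × (1 + 0.00763/0.6931) = 12.13 months.

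With an assumed 10% of death days missing, p falls to 0.00114 and the shift at m = 8 to about 0.01 month. At N = 300 that is 300 × 0.10 × 0.0114 = 0.3 patients. For scale, Protocol 9.5 gives a 95% CI of 6.732 to 9.435 months at N = 300 and a median of 8.

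**Step 5. Re-indexing to a later dose.** Suppose index moves d days later and patients who die before then leave the cohort. Under exponential survival with hazard λ, P(T − d > t | T > d) = exp(−λ(t + d))/exp(−λd) = exp(−λt). The distribution does not change: the later start shortens each survivor's OS by exactly enough to offset the lost early deaths.

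**The case against.** **Checks do exist.** A negative OS or duration is an obvious logic failure, and SAP 9.2 and 11 provide for logic checks, correction and review of distributions. This stands, so it would be wrong to say the plan has no check. What the visible text lacks is a date-order rule and a way to resolve a conflict. The checks are also weak against the first case, where no value looks wrong.

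**A rule may exist elsewhere.** Protocol 9.6 refers to a separate data management and review plan, and parts of the SAP's variable and exploratory-analysis text are not visible. A bounding rule there cannot be excluded. If there is one, SAP 9.4 need only refer to it.

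**The dates may be complete.** Neither document says that mortality-database or dose dates can lack a day. This stands. The size of the problem is unknown, although a partial index date alone can put death before index.

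**A reader might infer that the rule lengthens OS, because it removes or re-indexes early failures.** The documents do not support this as a material effect. Re-indexing leaves the median unchanged under the protocol's own exponential assumption (step 5). Dropping reversed deaths does push OS upward, but by about 0.1 month in the most extreme case (step 4). If the hazard changes over time, re-indexing could move the median in either direction.

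**Bounding has its own risk.** Moving an advanced diagnosis back to any same-month dose could turn an unlabelled perioperative dose into 1L and a Cohort 2 patient into a Cohort 1 patient. This stands and limits the fix.

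**Conclusion.** The point holds as a gap in the imputation rule. Followed as written, SAP 9.4 can reverse the order of dates on which 1L, cohort entry, line duration and OS depend, and the visible text does not say how a reversal is resolved.

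Reversal needs two dates in one calendar month with a day missing. Given that, about 21% to 27% of pairs reverse if ordered day pairs are equally likely. No overall percentage can be given with confidence, because the share of partial dates is not stated and the result depends heavily on the assumed lag distribution.

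The primary result is very unlikely to change. The effect falls mainly on line numbering, assignment to Cohort 1 or 2, diagnosis-to-1L time and duration of treatment. This is a minor refinement, worth making because it is cheap.

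**What to change.** Add to SAP 9.4, or cite the document where it already stands:

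- An imputed date is bounded by known dates in the same month.
- An imputed line stop is not before the start of that line or its last recorded dose.
- An imputed death is not before index or the last activity date.
- An imputed advanced diagnosis is not after a same-month systemic dose where the record supports that the dose was given for advanced disease.
- Same-month doses whose purpose is unclear are flagged and counted, and results are reported in a sensitivity analysis under both classifications.
- No patient is dropped because imputation produced a negative interval. Such intervals are set to a minimum of 1 day.

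Reporting the number of imputed dates by variable would also let a reader judge the size of the issue.

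The cost is a few sentences, a few lines of code, and flagging of a small number of ambiguous doses. Some bounded dates will be a few days off, as is already true of the 15th.

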6.3 STUDY POPULATION

Inclusion criteria:

- Patient has two or more documented clinical visits in the National Anti-Tumor Drug Surveillance System (NATDSS) network on or after January 1, 2013.
- Patient has a confirmed diagnosis of DDLPS during his/her lifetime.
- At least 18 years old at the date of initial diagnosis

No exclusion criteria are applied.

Eligible population will be divided into two groups:

- Cohort 1 will include unresectable locally advanced or metastatic DDLPS patients who received at least one line of systemic antineoplastic treatment by the end of cohort identification period (index date = start date of first line (1L) treatment).
- Cohort 2 will include patients with DDLPS who have not initiated 1L systemic antineoplastic treatment by the end of cohort identification period (index date = date of initial DDLPS diagnosis during cohort identification period). Patients initiated 1L treatment afterwards or patients received adjuvant and/or neoadjuvant therapy only through follow-up will be included in Cohort 2.

In both cohorts, 1L therapy will be defined as the initial set of drugs used after unresectable locally advanced or metastatic diagnosis. Metastatic patients will be defined as those with metastatic diagnosis or presence of metastatic sites; unresectable locally advanced patients will be defined as those with advanced diagnosis and without subsequent surgical resection.

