6.4 STUDY VISITS

Definitions of relevant time periods are detailed below.

Study period: January 1, 2013 – December 31, 2022

Baseline period: All available data prior to index date

Cohort identification period: January 1, 2013 – December 31, 2021 (one year before end of study period)

[figure not shown]
Statistical and Epidemiological Analysis Plan (SEAP) for Observational and Non-Interventional Studies (ONIS)

Index date: The index date for Cohort 1 will set to the date of initiation of 1L treatment; the index date for Cohort 2 will be the date of initial DDLPS diagnosis during cohort identification period.

Follow-up period: From index date until date of death, if available, or the date of censoring if there is no record of death, whichever occurs first. For survival and treatment patterns, the date of censoring will be the last activity date, defined as the date of the last visit of any type prior to the end of the study period.

Figure 1 illustrates the time periods for the study timelines.

(a). Cohort 1

(b). Cohort 2

[figure not shown]

Figure 1. Overall study period

Abbreviations: 1L = first line

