ANNEX 2. MOCK TABLE AND FIGURE

The following figures and tables will be developed for analyses of primary, secondary and exploratory objectives and will be replicated for subgroup analyses and sensitivity analyses, pending feasibility.

Table 1. Patient baseline demographic characteristics for Cohort 1 and Cohort 2

Demographic characteristics	Cohort 1	Cohort 2
Number of patients, N		
Index year, N (%) 2013		
2014		
2015		
2016		
2017		
2018		
2019		
2020		
2021		
Age at initial diagnosis, years		
$Mean \pm SD$		
Median (IQR)		
Min, Max		
Missing / Unknown		
Age (categorized) at initial diagnosis, N (%)		
<65		
≥65		
Missing / Unknown		
Age at index, years		
$Mean \pm SD$		
Median (IQR)		
Min, Max		

Statistical and Epidemiological Analysis Plan (SEAP) for Observational and Non-Interventional Studies (ONIS)

Page 21 of 36

Demographic characteristics	Cohort 1	Cohort 2
Missing / Unknown		
Age (categorized) at index, N (%)		
<65		
≥65		
Missing / Unknown		
Sex, N (%)		
Female		
Male		
Missing / Unknown		
Insurance type, N (%)		
National medical insurance		
Commercial insurance		
Out of pocket		
Others		
Missing / Unknown		
Region, N (%)		
Eastern China		
Central China		
Western China		
Northeast China		
Missing / Unknown		

Abbreviations: N = number; SD = standard deviation; IQR = interquartile range; min = minimum; max = maximum

Notes: Eastern China includes Beijing, Tianjin, Hebei, Shanghai, Jiangsu, Zhejiang, Fujian, Shandong, Guangdong, and Hainan; central China includes Shanxi, Anhui, Jiangxi, Henan, Hubei, and Hunan; western China includes Inner Mongolia, Guangxi, Chongqing, Sichuan, Guizhou, Yunnan, Tibet, Shaanxi, Gansu, Qinghai, Ningxia, and Xinjiang; northeast China includes Liaoning, Jilin, and Heilongjiang.

Statistical and Epidemiological Analysis Plan (SEAP) for Observational and Non-Interventional Studies (ONIS)

Page 22 of 36

Table 2. Patient clinical characteristics for Cohort 1 and Cohort 2

Clinical characteristics	Cohort 1	Cohort 2
Number of patients, N Year of initial diagnosis, N (%)		
Before 2013		
2013		
2014		
2015		
2016		
2017		
2018		
2019		
2020		
2021		
Missing / Unknown		
Disease stage at initial diagnosis, N (%)		
0		
I		
II		
III		
IV		
Missing / Unknown		
Histology, N (%)		
Dedifferentiated		
Other		
Missing / Unknown		
ECOG performance status, N (%)		
0		
1		
2		
3		
4		
Missing / Unknown		

Statistical and Epidemiological Analysis Plan (SEAP) for Observational and Non-Interventional Studies (ONIS)

Page 23 of 36

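### Year-only dates are left missing with no fallback, so a death known only to the year has no event time and a diagnosis known only to the year has no start time.

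*SAP*

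**What the plan says.** SAP 9.4 states the general principle "Only partial missing dates will be imputed, and no replacement/imputation procedures will be used for defined variables" and then gives two rules. The first is "If the day is missing and the month and year is complete, the day will be imputed as the 15th of the month". The second is "If day and month or year was missing, the date will not be imputed and will be reported as missing". The wording of the second can be parsed in two ways, but under either a date with a known year and no month stays missing.

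Three analyses need a full date:

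- **Primary OS (SAP 10.1.1).** "For OS calculation, the event time is the date of death recorded by the National Mortality Database from CDC".
- **Survival after initial diagnosis (SAP 7.1.2).** This is death date minus diagnosis date, so it needs both.
- **Cohort 2 (SAP 6.4).** "the index date for Cohort 2 will be the date of initial DDLPS diagnosis during cohort identification period".

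The OS censoring rule covers one group only: "Patients without death record during the study period will be censored at the last medical record during the study period". SAP 6.4 and 7.1.1 limit censoring in the same way. Protocol 9.7 says only that partial dates are imputed, without giving rules.

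**The concern.** A patient recorded as having died in, say, 2019, with no month, fits neither branch of the OS rule. There is a death record, so the patient is not to be censored; there is no usable date, so the patient cannot be an event. Someone will have to decide at programming stage, after the data are visible.

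Only patients who died can have an incomplete death date, so the loss depends on the outcome. Dropping or censoring these patients both push the median up. Protocol 9.9 already expects survival to be over-estimated because mortality surveillance may capture only 80% of deaths, and this would add to it.

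For diagnosis dates the stake is patients rather than events: a Cohort 2 patient with a year-only diagnosis has no index date and no place on the survival-after-diagnosis curve.

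**Working it through.** **Inputs from the documents.** Protocol 9.5: exponential survival with median 8, 10 or 12 months, uniform enrolment, about 20% censored. SAP 6.4: index dates from 2013 to 2021, data to the end of 2022. SAP 10.1.1: Kaplan-Meier median, log-log interval.

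**Assumptions.** The documents do not give the share p of deaths known only to the year, nor the time from last record to death. I take p from 1% to 10%, and a mean gap of 1 or 2 months.

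**The plan's own figure.** Simulating the protocol 9.5 precision table with uniform censoring at 20% (300 replicates per cell) gives 9.290 to 10.800 for N=1500 and median 10, against the stated 9.262 to 10.784. All 12 rows agree within 0.6%. That table is sound and is not at issue.

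**Censoring known deaths, by formula.** If a share p of deaths is censored shortly before death, the observed hazard falls to (1 − p) times the true one. The median becomes about m / (1 − p):

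- p = 1%: 10 / 0.99 = 10.10
- p = 2%: 10 / 0.98 = 10.20
- p = 5%: 10 / 0.95 = 10.53
- p = 10%: 10 / 0.90 = 11.11

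**Dropping, by reasoning.** If everyone were followed to death, removing a random share of deaths would leave the survival distribution unchanged. Bias arises only because patients still alive at censoring are not thinned in the same way, so the shift should be small.

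**Simulation, true median 10 months.** Set-up A has no loss before the end of 2022, a 1-month gap and mid-year dating not earlier than the last visit (n = 300,000). Set-up B has random loss giving about 17% censored, a 2-month gap and the bounded midpoint described in the fix (n = 400,000).

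| Set-up | p | Censored at last record | Dropped | Kept as event, dated |
|---|---|---|---|---|
| A | 1% | 10.09 | 9.99 | 9.99 |
| A | 5% | 10.48 | 10.10 | 10.07 |
| A | 10% | 11.05 | 10.13 | 10.13 |
| B | 2% | 10.2 | 10.04 | 10.05 |
| B | 5% | 10.5 | 10.1 | 10.1 |
| B | 10% | 11.0 | 10.2 | 10.2 |

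In set-up A at p = 10%, the share of patients with an event falls from 0.941 to 0.848 under dropping, a loss of 0.093 / 0.941 = 9.9% of events. At true medians of 8 and 12, censoring gives 8.81 and 13.32 (+10% and +11%), and dropping gives 8.06 and 12.15 (about +1%).

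**Two-end rerun.** A further run at p = 10% and true median 10 gave 10.95 censored, 10.18 dropped and 10.21 at the bounded midpoint. Dating the affected deaths at the earliest and latest possible day gave 9.87 and 10.73, which bracket the true 10.

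**Diagnosis dates.** The identification period is made of whole calendar years, so the year alone settles whether a diagnosis falls inside it. The year also settles the criterion "At least 18 years old at the date of initial diagnosis" for everyone except those who turn 18 in that year.

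**The case against.** **Censoring recorded deaths would breach the SAP.** This is correct. The larger figures describe an error the OS text does not permit, so they are not the effect of the rule as written. The risk remains because an empty death date looks the same in code as no death, and SAP 10 describes losses to follow-up as patients alive at their last visit, which every patient who later died also was.

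**Against dropping, a midpoint date does not reduce bias.** This stands: the two columns agree to within about 0.03 months. Not imputing is also defensible in itself, since a midpoint can be wrong by up to about 6 months against planning medians of 8 to 12.

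**Nothing shows that such dates occur.** This stands too. OS deaths come from a mortality database whose date completeness is not described, and the effect may be negligible.

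**The comparison with the precision table is selective.** At p = 10%, 11.0 months lies above the stated upper limit for N=1500 (10.784) but below those for N=500 (11.378) and N=300 (11.814).

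**Part of this is already covered.** SAP 9.4 and 10 commit to counting missing values and discussing their impact. Protocol 9.5 planned for no power target. These limit the harm but do not say how an undated death enters the curve.

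A reader might also infer that a known year is removed from the Table 2 row "Year of initial diagnosis, N", or that a patient with a known diagnosis year fails the age criterion. The documents do not say either. SAP 9.4 makes the date missing, the year is a separate row, and derivation rules may lie in the blanked variable pages.

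**Conclusion.** The point holds as a gap in the handling rule. SAP 9.4 leaves year-only dates missing, the survival definitions need full dates, and the OS censoring rule covers only patients without a death record.

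A reader might go further and conclude that the plan censors known deaths, or that it necessarily removes events and inflates OS by 10%. The text does not support that: it leaves the handling open, and the two possible readings differ widely. With a true median of 10 months, exponential survival and an assumed 10% of deaths known only to the year, dropping gives about 10.2 months with about 10% of events lost, and censoring gives about 11.0. At 1–2% the shift is about 2% or less either way. The actual share is unknown.

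The change is worth making because it is cheap, concerns the primary outcome and settles the choice before results are seen. It should not be presented as a bias correction relative to dropping.

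**What to change.** In SAP 9.4 and 10.1.1:

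1. **Deaths.** A death whose known year lies in the study period is kept as an event and never censored. Date it at the midpoint between two bounds: the later of the last activity date and 1 January of that year, and 31 December of that year.
2. **Bounds.** Rerun primary OS with all such deaths at the early bound, then at the late bound.
3. **Diagnosis.** Use a known year directly for the Table 2 year row, for the identification-period check, and for the age check where the year settles it. State how patients with a year-only diagnosis enter or leave survival after diagnosis and Cohort 2.
4. **Reporting.** Give the number of year-only dates separately for death, initial diagnosis and 1L start. Dates with no year stay missing.

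The cost is a few sentences and a few lines of code. The downside is a dating error of at most about 6 months in the affected patients, whose effect the two-end rerun shows.
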